4.3. Exclusion Criteria

Subjects will not be permitted to enroll in the study if any of the following criteria apply:

- 1. Requires mechanical ventilation
- 2. Current participation in any other interventional study.
- 3. Alanine transaminase/aspartate transaminase levels (ALT/AST) ≥3times the upper limit of normal (×ULN) or total bilirubin (Tbili) ≥2×ULN.
- 4. Lymphocyte count <500 lymphocytes/μL or hemoglobin <11.0 g/dL
- 5. Stage 4 severe chronic kidney disease or requiring dialysis (ie, estimated glomerular filtration rate <30)
- 6. Any other condition, that in the opinion of the investigator, may be cause to exclude the subject from the study.

- 7. Use of steroids (except dexamethasone), sensitive CYP2D6 substrates, CYP2C inducers, IL-6 neutralizing antibodies, IL-6 receptor inhibitors, or any investigational therapy.
- 8. Pregnancy or breast feeding.
- 9. Anticipated transfer to another hospital which is not a study site within 72 hours.
- 10. Known allergy to PTC299 or excipients.

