8.4.4.5. Laboratory Parameters

Changes in clinical laboratory tests from baseline (last measurement prior to first dose) and laboratory marked abnormalities using pre-defined abnormality criteria will be descriptively summarized.

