#### **Normalization in the complete blood count**

Normalization of complete blood count is defined as all blood components such as WBC, RBC, HGB, HT, HCV, HCH, HCHC, and platelets return to the lab normal range post baseline during the study for subjects who had out of the normal range value of any of the blood component at baseline.

Number and percentage of subject achieving normalization of complete blood count in subjects with abnormal complete blood count at baseline will be summarized by treatment groups.

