#### **4.10.1. Adverse Events**

All adverse events (AEs) will be coded using the MedDRA. The MedDRA version will be indicated in the footnote of relevant AE tables based on the current version used in the clinical data.

AEs will be analyzed in terms of treatment-emergent adverse events (TEAEs), which are defined as any AEs that occurring on or after the first study treatment through 30 days after the last dose, or any AEs occurring before the first study treatment but worsening during the treatment through 30 days after the last dose.

A treatment related TEAE is defined as TEAE that is suspected (possibly or probably related) by the investigator to be related to the study treatment. The severity/intensity of AEs will be graded 1 to 5 according to the National Cancer Institute (NCI) Common Terminology Criteria for Adverse Events (CTCAE) version 5.0. For AEs not described in CTCAE criteria, the intensity will be assessed by the investigator as mild (Grade 1), moderate (Grade 2), severe (Grade 3), life threatening (Grade 4), and fatal (Grade 5).

An overview of TEAE summary by treatment groups table will be provided with following information:

- The number of subjects with at least one TEAE
- The number of subjects with at least one treatment related TEAE
- The number of subjects with at least one Grade 3 or Grade 4 TEAE
- The number of subjects with a Grade 5 TEAE (Fatal)
- The number of subjects with at least one SAE

The number of subjects with at least one TEAE leading to treatment discontinuation.

All TEAEs will be summarized by MedDRA system organ class (SOC), and PT. If a subject experiences multiple AEs under the same SOC, the subject will be only counted once for the SOC with the greatest severity. Similarly, if a subject experiences multiple AEs under the same PT and SOC, the subject will be counted only once for the PT with the greatest severity.

The table will be sorted by the descending order of the frequency of SOC then by the descending order of the frequency of PT under SOC based on the PTC299 column.

In addition, the following summary tables will be provided:

- All TEAE by descending frequency of PT
- All TEAE by maximum severity under each SOC and PT
- SAE by SOC and PT
- Treatment related TEAE by SOC and PT
- TEAE leading to treatment discontinuation by SOC and PT

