#### 4.10.4. Clinical Laboratory Evaluations

Laboratory values will be presented in standard units. If any assessment is performed at both local and central laboratories, the value from central laboratory will be used in the analysis. In the event of repeated values for a test at a visit from same laboratory, the last non-missing value at that visit will be used

Descriptive statistics will be provided for each clinical laboratory parameter at baseline, at each study visit post baseline for actual values and changes from baseline by treatment groups. Unless otherwise specified, only scheduled visits will be included in the summary tables.

Clinical laboratory values will be graded according to NCI CTCAE version 5.0 for applicable tests. A summary table of the worst CTC grade post baseline during the treatment period of laboratory data will be provided by treatment groups. For the worst CTC grade tables, unscheduled laboratory values will be considered as well.

A by-subject listing will also be provided for laboratory data. Laboratory values that are outside the normal range will also be flagged in the data listings. Any out-of-range values that are identified by the investigator as being clinically significant will also be shown in a listing.

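### The one CTC-graded laboratory table leaves out baseline grade, so abnormalities carried in from entry dilute the relative contrast between arms for lower grades and for tests without an entry limit

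*SAP*

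**What the plan says.** SAP 4.10.4 plans these laboratory safety outputs:

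- One graded table: "A summary table of the worst CTC grade post baseline during the treatment period of laboratory data will be provided by treatment groups". The next sentence adds "For the worst CTC grade tables, unscheduled laboratory values will be considered as well".
- Descriptive statistics "at each study visit post baseline for actual values and changes from baseline by treatment groups", limited to scheduled visits unless otherwise specified.
- By-subject listings that flag out-of-range values.

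SAP 4.10.4.1 (Table 1) adds categories of ALT, AST and bilirubin in multiples of ULN, and SAP 4.10.3 adds the hepatic AESI criteria. Neither carries a baseline condition. Protocol 8.4.4.5 plans summaries of "Changes in clinical laboratory tests from baseline (last measurement prior to first dose) and laboratory marked abnormalities using pre-defined abnormality criteria". Here baseline applies to the changes, and nothing ties a marked abnormality to the value at entry.

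For adverse events the SAP does use the pre-treatment state. An event already present before dosing is treatment-emergent only if it belongs to "any AEs occurring before the first study treatment but worsening during the treatment through 30 days after the last dose" (SAP 4.10.1).

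The plan expects abnormal baselines. The blood-count normalization endpoint in SAP 4.9.2.2 is defined "for subjects who had out of the normal range value of any of the blood component at baseline". Protocol 4.3 excludes the more extreme values, with criteria such as "Lymphocyte count <500 lymphocytes" per μL and "or total bilirubin (Tbili) ≥2×ULN", together with ALT/AST of 3×ULN or more and hemoglobin below 11.0 g/dL. It sets no limit for platelets, total WBC or ALP.

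**The concern.** A subject who enters with a low-grade abnormality and never changes falls in the same cell of the worst-grade table as a subject who reaches that grade on study drug. In hospitalized COVID-19 patients, some blood-count and chemistry abnormalities will come from the illness. They add a similar number to both arms and carry no information about the drug.

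The other outputs do not replace a baseline-aware graded count. By-visit change summaries describe groups, not individual grade shifts, and leave out unscheduled values. Listings support case review but not a comparison of arms. Under Protocol 7.5.1, laboratory abnormalities that need neither intervention nor further investigation are not reported as AEs, so the TEAE rule never reaches them. For those, the laboratory tables are the only aggregate evidence. What is at stake is how readily a modest excess of lower-grade changes can be seen, in a trial that singles out liver and blood-count safety in Protocol 6.1.1 and 6.1.2.

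**Working it through.** The documents state no figure for this point, so there is nothing to reproduce. The check has two parts.

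**Where can baseline abnormality enter the count?** Let b be the share of subjects already in a grade category at baseline.

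| Level | Entry limit (Protocol 4.3) | b for eligible subjects |
|---|---|---|
| ALT/AST >5×ULN (Grade ≥3 in Protocol 7.5.3; hold level in 6.1.1) | below 3×ULN | about 0 |
| ALT/AST >3×ULN (lowest row of SAP Table 1) | below 3×ULN | about 0 |
| Bilirubin >2×ULN (hold level, AESI, Table 1) | below 2×ULN | about 0 |
| Lymphocytes <500/μL (hold level in 6.1.2) | at least 500/μL | about 0 |
| Hemoglobin <11.0 g/dL (hold level in 6.1.2) | at least 11.0 g/dL | about 0 |
| ALP ≥2×ULN (AESI) | none | can exceed 0 |
| Platelets, total WBC | none | can exceed 0 |
| Lower grades of the limited tests | milder values admitted | can exceed 0 |

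The concern is therefore confined to the last three rows.

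**How large is the dilution there?** Inputs: n = 190 per arm (Protocol 4.1). Assumed: new onset p = 12% on PTC299 and 4% on placebo among subjects unaffected at baseline; b equal in both arms; every baseline abnormality persists in its category.

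- Planned table: rate = b + (1 − b)p.
- Count of grade increases over all subjects: rate = (1 − b)p.
- In both counts the risk difference is (1 − b)(0.12 − 0.04).

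| b | Planned table | Ratio | Grade increases | Ratio | Risk difference, both |
|---|---|---|---|---|---|
| 10% | 20.8% vs 13.6% | 1.53 | 10.8% vs 3.6% | 3.0 | 7.2 points |
| 30% | 38.4% vs 32.8% | 1.17 | 8.4% vs 2.8% | 3.0 | 5.6 points |
| 50% | 56.0% vs 52.0% | 1.08 | 6.0% vs 2.0% | 3.0 | 4.0 points |

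The added noise shows in the standard error of the difference. At b = 30%:

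- Planned table: √[(0.384×0.616 + 0.328×0.672)/190] = 4.9 points.
- Grade increases: √[(0.084×0.916 + 0.028×0.972)/190] = 2.3 points.

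As a measure of visibility only, since these tables carry no test, nominal two-sided 0.05 power with 190 per arm would be:

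| b | Planned table | Grade increases |
|---|---|---|
| 10% | 46% | 78% |
| 30% | 21% | 66% |
| 50% | 12% | 51% |

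A second assumption, new onset 20% versus 10%, gives the same pattern. A true ratio of 2.0 appears as 1.47, 1.29, 1.19 or 1.09 at b = 10%, 20%, 30% or 50%. At b = 0 the two counts coincide.

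**The case against.** A reader might infer that the planned table hides a drug effect or biases the comparison. The documents do not support that. Allocation is randomized, so baseline abnormalities balance on average, and the risk difference is identical in the two counts, as shown above. The table is also laid out by grade, so movement to a higher grade remains visible.

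Nor does the concern reach the levels at which the protocol acts. The hold levels in Protocol 6.1.1 and 6.1.2, the ALT, AST and bilirubin rows of SAP Table 1, and every AESI criterion except ALP sit at or beyond an entry limit. An eligible subject who crosses one of them has worsened since screening. The HAC also reviews liver cases individually. Laboratory changes that need intervention or further investigation are generally reported as AEs and then come under the TEAE rule. All of this stands and sets the limits of the point.

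It is also fair that the assumed rates are not in the documents, that persistence of every baseline abnormality is the simplest case, and that the CTCAE text is not reproduced. Apart from Grade ≥3 ALT and AST, the documents do not show which admitted entry values carry a grade.

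What does not stand is that other outputs close the gap. Minimum and maximum change at scheduled visits, flagged listings and marked-abnormality counts do not give the number of subjects per arm whose grade rose.

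**Conclusion.** The point holds in a limited form. The one CTC-graded laboratory table mixes persisting entry abnormalities with new or worsened ones, and this departs from the SAP's own rule for adverse events. The consequence is a diluted ratio and a noisier difference for lower grades and for tests without an entry limit. No bias in the risk difference follows, and levels at or beyond the entry limits are largely unaffected.

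Under the assumed 12% versus 4%, a true ratio of 3.0 appears as 1.53 to 1.08 as baseline prevalence goes from 10% to 50%. The size depends wholly on baseline prevalence, onset rates and persistence, which the documents do not give. The change is worth making because it uses data already collected and brings laboratory reporting into line with SAP 4.10.1.

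**What to change.** In SAP 4.10.4:

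- Add, for each gradable test and each arm, a table of baseline grade by worst post-baseline grade, using scheduled and unscheduled values as the present table does.
- Report the number and percentage of subjects whose worst post-baseline grade exceeds their baseline grade.
- Show subjects with missing baseline in a separate row. Setting them to grade 0 would count unknown pre-existing abnormalities as emergent.
- Keep the existing worst-grade table as the margin of the new one.

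The cost is SAP wording and one extra dimension in a planned table. Baseline is already defined in SAP 6.1 and the pre-dose values are in the schedule of events, so no new data are needed and no clinical rule changes.

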##### 4.10.4.1. Liver Related Laboratory Parameters

The liver function related parameters will be assessed and summarized. The potential Hy's law cases (as serum ALT or AST >3xULN and total bilirubin >2xULN) will be evaluated and summarized based on the criteria listed in Table 1:

**Table 1: Liver Function Test Result Categories**

Parameter	Criteria
ALT	>3ULN and <=5ULN >5ULN and <=8ULN >8ULN
AST	>3ULN and <=5ULN >5ULN and <=8ULN >8ULN
Total Bilirubin	>2ULN >3ULN
Total Bilirubin>2ULN and ALT	>3ULN and <=5ULN >5ULN and <=8ULN >8ULN
Total Bilirubin>2ULN and AST	>3ULN and <=5ULN >5ULN and <=8ULN >8ULN

#### 4.10.5. Vital Signs

Vital sign parameters will be summarized for both actual and change from baseline values by study visit, by treatment groups.

Vital signs will also be listed.

#### **4.10.6. Physical Examination**

Physical examination results will be presented in a by-subject listing.

#### **4.11. Subgroup Analysis**

To evaluate treatment effect in a more homogeneous population, the primary endpoint will be explored within the following subgroups as deemed appropriate:

- Age ( $\leq 62$  vs  $>62$ )
- Remdesivir use (yes vs no)
- Dexamethasone use (yes vs no)
- Chronic kidney disease (yes vs no)
- COPD/asthma (yes vs no)
- Immunocompromised (yes vs no)
- Type 2 diabetes (yes vs no)
- Heart disease (yes vs no)
- Sickle cell disease (yes vs no)
- Obesity (yes vs no)
- Hypertension (yes vs no)
- Days from symptom to randomization less than or equal to 5 days (yes vs no)

If any of the subgroup levels has less than 10% of subjects the subgroup analysis will not be performed.

The treatment effect in the subgroup analysis will be evaluated by an un-stratified log-rank test and the hazard ratio will be estimated using the unstratified Cox proportional hazards model.

The subgroup analysis will be performed in ITT population in each subgroup.

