8.4.7. Subgroup Analyses

Subgroup analyses of the primary endpoint by baseline disease risk factors will be explored as deemed appropriate. In such analyses, an un-stratified log-rank test and the hazard ratio will be estimated using the unstratified Cox proportional hazards model.

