## **4. STATISTICAL CONSIDERATIONS**

### **4.1. General Methods and Reporting Conventions**

Data will be summarized by treatment groups. Categorical variables will be summarized by frequency distributions (number and percentage of subjects). A missing category will be created for subjects with missing information. If no subjects in a category for a categorical variable, the category will be presented with zero count. Continuous variables will be summarized by descriptive statistics (such as number of subjects, mean, standard deviations, median, minimum, maximum, and number of missing if any). All tests of hypotheses will be considered nominally statistically significant if the 2-sided p-value is less than 0.05 or a pre-specified significance level.

Statistical analyses will be performed using the Statistical Analysis System (SAS) version 9.4 or higher.

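### Subgroup effects are tested within each level of up to twelve factors but never compared between levels, so a chance split in p-values can be misread as effect modification

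*SAP*

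**What the plan says.** SAP 4.11 names twelve factors with two levels each: the three stratification factors, eight disease risk factors, and time from symptoms to randomization cut at 5 days. The revision history shows that the last of these was added in version 3.0.

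On method, SAP 4.11 states: "The treatment effect in the subgroup analysis will be evaluated by an un-stratified log-rank test". It also calls for a Cox hazard ratio, again without stratification, and adds: "The subgroup analysis will be performed in ITT population in each subgroup". Protocol 8.4.7 likewise names "an un-stratified log-rank test and the hazard ratio will be estimated using the unstratified Cox proportional hazards model".

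Three statements limit the scope:
- Under SAP 4.11, "the primary endpoint will be explored within the following subgroups as deemed appropriate".
- Also in SAP 4.11: "If any of the subgroup levels has less than 10% of subjects the subgroup analysis will not be performed". Twelve is therefore a maximum.
- SAP 4.1 says that tests "will be considered nominally statistically significant if the 2-sided p-value is less than 0.05" or below another pre-specified level.

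SAP 4.9 sets efficacy tests at two-sided 0.05, with p-values and 95% CIs. Neither document mentions an interaction test, a multiplicity adjustment or an interpretation rule for subgroups. The nearest candidate is the third sensitivity analysis in SAP 4.9.1.1. It adds time from symptom onset, cut at 7 days, as a further variable in the primary model and is not described as an interaction.

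**The concern.** Each level of each factor receives its own p-value against 0.05. A reader who sees p<0.05 in one level and not in the other will tend to conclude that the drug works in the first group and not in the second. That conclusion does not follow. The two p-values answer two separate questions, and each depends heavily on the number of events in its level. Whether the two effects differ is a third question, which the plan does not ask.

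What is at stake is the reading of the subgroup table. If one group looks favourable, for example those randomized within 5 days of symptoms, the planned output contains no direct comparison to show whether the contrast exceeds what chance would give.

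**Working it through.** **Inputs from the documents.** SAP 3.6 and Protocol 8.2: 326 events, more than 80% power, hazard ratio 1.38, two-sided 0.05, medians of 11 and 8 days, Day 28 improvement rates of 0.829 and 0.912, about 380 subjects. SAP 3.1: 1:1 allocation. SAP 3.7: futility bound at hazard ratio 1.091 with 163 events.

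**Step 1: reproduce the design.**
- Hazard ratio from the medians: 11/8 = 1.375.
- Day 28 rates under exponential times: 1 − 2^(−28/11) = 0.829 and 1 − 2^(−28/8) = 0.912.
- Power = Φ(√(D/4) × ln HR − 1.96). With D = 326 this gives 82.0% at 1.375 and 82.8% at 1.38. Applying the futility bound gives 80.0% and 80.9%.
- Subjects: 326 / 0.8705 = 375, against about 380.

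The plan's figures reproduce, so the same formula can be used within levels.

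**Step 2: one factor, same effect in both levels.** Take HR = 1.375 throughout and a 50/50 split, so D = 163 per level.
- √(163/4) × ln 1.375 = 6.384 × 0.3185 = 2.033.
- Power per level = Φ(2.033 − 1.96) = 0.53.
- The levels contain different subjects, so P(exactly one significant) = 2 × 0.53 × 0.47 = 0.50.

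**Step 3: uneven splits.** With power p₁ and p₂ in the two levels, P(exactly one) = p₁(1 − p₂) + p₂(1 − p₁).

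| Split of events | Events per level | Power per level | Exactly one level p<0.05 |
|---|---|---|---|
| 50/50 | 163 / 163 | 0.53 / 0.53 | 50% |
| 30/70 | 98 / 228 | 0.35 / 0.67 | 55% |
| 20/80 | 65 / 261 | 0.25 / 0.73 | 61% |
| 10/90 | 33 / 293 | 0.15 / 0.78 | 70% |

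The 10% rule in SAP 4.11 still allows the last row. Because the effect is the same in both levels, an interaction test at 0.05 rejects 5% of the time in every row.

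**Step 4: what an interaction test can detect.** The variance of the log ratio of hazard ratios is about 4/D₁ + 4/D₂. For 80% power the ratio must reach exp[(1.96 + 0.8416) × √(4/D₁ + 4/D₂)]. At 163/163 this is exp(2.8016 × 0.2215) = 1.86. It is 1.97 at 30/70, 2.17 at 20/80 and 2.81 at 10/90.

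**Step 5: multiplicity of interaction tests.** With no effect modification and independent factors, the chance of at least one unadjusted interaction p<0.05 is 1 − 0.95^11 = 43% for eleven factors and 1 − 0.95^12 = 46% for twelve.

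**The case against.** The strongest reply is that these analyses are exploratory and discretionary, that significance is only nominal, and that success is tied solely to the primary test in the ITT population (Protocol 8.1, SAP 4.9). SAP 4.11 gives its aim as assessing the effect in more homogeneous groups, which is estimation within groups, and nowhere says that one significant and one non-significant level shows a difference. All of this stands. A reader might infer that the method is bound to generate subgroup claims, but the documents do not support that: no claim is made to depend on a subgroup p-value. The supportable statement is that the output can be misread and that the comparison which would guard against this is absent.

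A reader might also point to the false-positive rate when the drug has no effect at all. In simulation with twelve independent factors and assumed prevalences of 15% to 50%, at least one level reached p<0.05 in about 45% to 50% of trials. That figure is no argument for interaction tests. They leave nearly the same chance of at least one false positive (Step 5), because it is a matter of multiplicity. Only the uniform-effect calculation in Steps 2 and 3 supports the change.

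Part of what is needed is already planned, since subgroup hazard ratios are specified in SAP 4.11 and CIs in SAP 4.9. Finally, Protocol 8.4.7 itself names the within-subgroup log-rank test. Deleting it in SAP 4.11 alone would depart from the protocol and contradict SAP Section 5, which reports no change. That objection stands and shapes the fix.

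**Conclusion.** The point holds as a gap in an exploratory analysis. The plan tests treatment within each level of up to twelve factors and never tests whether the effect differs. With the sponsor's own design effect applying uniformly, a single factor shows one significant and one non-significant level in about 50% of trials at an even split and up to about 70% at 10/90, against 5% for an interaction test.

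This rests on the planned 326 events being reached, a uniform hazard ratio of 1.375, 1:1 allocation within levels, and the usual normal approximation to the log-rank statistic. The documents give no prevalences for the factors, so the splits are shown as a range. The per-factor result does not depend on how many factors survive the 10% rule.

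Severity is low to moderate: the type I error and conclusion of the primary analysis are unaffected.

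**What to change.** In SAP 4.11:
- For each factor analysed, fit a Cox model with treatment, factor and their interaction. Report the ratio of hazard ratios with its 95% CI and the interaction p-value beside the subgroup hazard ratios and CIs.
- State that any remark that effects differ between levels rests on the interaction, not on the within-level p-values.
- Label the results exploratory and state how many factors were examined.

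In SAP Section 5, record the addition. The within-level log-rank test can stay as a descriptive result, or be removed by a change that is also recorded there, since Protocol 8.4.7 names it.

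The cost is a few lines of text and code, with no effect on trial conduct or the primary analysis. There are two downsides. Power is low: even at a 50/50 split, 80% power needs a ratio of hazard ratios of about 1.86, so a non-significant interaction must not be read as evidence of a uniform effect. Multiplicity also remains, at about 43% to 46% for at least one p<0.05 over eleven or twelve unadjusted tests, which is why the number of factors should be reported.
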